Adults age 18 to 60 are being recruited via online advertisements, newspaper, flyers, and referrals from local clinics within the community since July 2015. Inclusion criteria are: (a) meet DSM-5 criteria for BN or BED refractory to prior treatment, (b) have a BMI of 21 or greater, (c) if female with child-bearing potential, must have an initial negative pregnancy test and have adequate birth control measures, (d) must be medically stable with no new diagnoses (medical, surgical, or psychiatric) within the past 6 months, (e) must be able to comply with all 12 study visits, treatment plans, and blood draws at Stanford. Exclusion criteria include: (a) any patient with bipolar disorder or schizophrenia, any patient taking a mood stabilizer or antipsychotic medication within the past 3 months of enrollment, or any patient on an unstable SSRI dose (change in dosage over the prior 30 days), (b) any patient with current or past history of anorexia nervosa (including BMI < 17.5), (c) any history of prior (within 30 days) use of over the counter weight-reducing agents or herbal preparations, (d) any prescription weight loss medication within 3 months of enrollment, (e) any patient who started a psychological weight-loss intervention (e.g. Weight Watchers, Jenny Craig) within the prior month or if started over a month and achieved weight loss, (If no weight loss was achieved in over a month, eligibility was considered provided willingness to discontinue the weight intervention) (f) currently receiving

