therapy with a psychostimulant or used a psychostimulant within past 6 months of enrollment, (g) any known sensitivity to phentermine or topiramate, (h) change in thyroid, psychiatric (e.g., antidepressant), or blood pressure medications within the past one month, (i) on a potassiumwasting diuretic, (i) on a carbonic anhydrase inhibitor such as zonisamide or acetazolamide, (k) on insulin or an insulin secretagogue, (1) liver enzymes at baseline greater than three times the upper limit of normal, (m) any baseline potassium of less than 3.0 milliEquivalents/liter, (n) abnormal baseline Thyroid Stimulating Hormone (TSH) greater than 1.5 times the upper limit of normal, (o) any patient unwilling or expressing uncertainty about being able to refrain from daily alcohol use (even if at moderate levels) or illegal drugs while taking the study medication, including medical marijuana, (p) any recent history of suspected substance abuse or dependence, (q) history of misuse of a stimulant, (r) current suicidal ideation or baseline Patient Health Questionnaire (PHQ-9) score of 20 or greater, (s) history of nephrolithiasis, (t) is pregnant or who is planning to become pregnant during the study period, (u) unable to identify a primary care physician, (v) history of cardiovascular disease (i.e. recent history of myocardial infarction, stroke, shortness of breath, chest pain) that could increase vulnerability to the sympathomimetic effects of a stimulant-like drug.

Screening/Enrollment

Eligibility is assessed via an initial telephone screen to determine whether DSM criteria for BED or BN are met and whether any inclusion/exclusion criteria as detailed are/are not satisfied. Those who do not meet criteria are provided with a referral list for treatment/care. Those who meet criteria on initial screening are asked to complete baseline assessments, including labs and written informed consent, prior to invitation for an in-person clinical interview. The assessments are completed again after treatment in the first medication group, at baseline 2 prior to crossing over to the second medication group, and then after completion of the second medication group. Labs completed at baseline include complete blood count, complete metabolic panel, TSH, and if female, a pregnancy test. At study physician's discretion, additional labs may be ordered during the study as clinically appropriate.

Safety/Tolerability

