Inclusion and exclusion criteria during the screening process will help to exclude patients who might suffer side effects from the treatment (e.g., low potassium) while assuring that those entered will have the appropriate diagnosis to possibly benefit from this treatment. At the first study visit, the study physician reviews all inclusion/exclusion criteria as well as all labs again. Any female with confirmed or intended pregnancy is informed and excluded due to potential teratogenicity. Women are counseled specifically that the extra risk of cleft lip and/or palate when taking topiramate during the first trimester is 1 in 500. Physician investigators involved in prescribing Qsymia have taken the REMS training program offered by Vivus (Campbell, CA) in an effort to reduce risk of teratogenicity for women of childbearing potential. The need for consistent use of effective contraception during treatment is encouraged. All participants are given information about Qsymia and the most common side effects at the top doses (e.g., tingling/parasthesias, constipation, dry mouth, abnormal taste, dizziness, insomnia, nausea, depression, blurred vision, low potassium, and angle closure glaucoma [less than 1 in 1000]). ⁴⁴

To improve the likelihood of safety during the trial, any patients with baseline potassium levels between 3.0-3.5 milli-equivalents/liter would be encouraged to ingest foods higher in potassium. To reduce the risk of side effects such as insomnia, patients are instructed to take Qsymia in the morning, with or without food. To reduce the risk of renal stones, parasthesias, or dry mouth, patients are instructed to drink 8 glasses of water per day. Patients are told to report any symptoms of blurred vision and/or eye pain. In such cases Qsymia is discontinued and patients are referred for intra-ocular pressure measurement within one day of symptom onset.

Measures

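### Birth control is required at entry but only encouraged on treatment, and no visible text makes it a condition of dosing, including at the week-14 crossover

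*Combined protocol and SAP*

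**What the plan says.** **Entry.** In Participants: Inclusion/Exclusion Criteria, inclusion (c) reads "if female with child-bearing potential, must have an initial negative pregnancy test and have adequate birth control measures". Exclusion (t) removes anyone who "is pregnant or who is planning to become pregnant during the study period". Inclusion (e) asks that participants "must be able to comply with all 12 study visits, treatment plans, and blood draws at Stanford".

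**First visit and counselling.** Safety/Tolerability says: "At the first study visit, the study physician reviews all inclusion/exclusion criteria as well as all labs again". It continues: "Any female with confirmed or intended pregnancy is informed and excluded due to potential teratogenicity". Women are told that "the extra risk of cleft lip and/or palate when taking topiramate during the first trimester is 1 in 500", and prescribers have taken REMS training.

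**During treatment.** The only sentence on contraception is in the same section: "The need for consistent use of effective contraception during treatment is encouraged".

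**Reassessment.** Screening/Enrollment lists the pregnancy test among the baseline labs and leaves further labs to the study physician's discretion. It also says: "The assessments are completed again after treatment in the first medication group, at baseline 2 prior to crossing over to the second medication group".

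**Schedule and dosing.** Table 2 has no row for contraception, pregnancy testing or labs at any visit. Methods Procedure and the Discussion let the dose depend on effect and side effects, and do not mention contraception.

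**The concern.** The written rule is strongest at entry and weaker while the drug is being taken. The plan itself calls the drug potentially teratogenic. Followed as written, it would let a woman whose contraception has lapsed start or continue study medication, provided she is neither pregnant nor intending to be. Unintended pregnancy is what a contraception requirement exists to prevent.

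The crossover lengthens the interval. Participants randomized to placebo first meet active drug only in the second period, well after the last written review. If the study physician is blinded, as the double-blind design implies, he or she cannot know that week 14 is a first exposure for a given woman. Any re-check therefore has to be a rule applied to everyone.

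**Working it through.** The plan gives no statistical figure on this point, and significance level, power and sample size are unaffected. The check is a timeline and a comparison of texts.

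**Timeline.** Inputs are the 12-week periods and 2-week washout (Methods Procedure) and the visit weeks in Table 2. First period-2 dose: 12 + 2 = week 14, which matches Medication Visit 6. The last written review of the criteria is at week 0.

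- Active-first: active dosing from day 0 to 12 × 7 = day 84 after the review.
- Placebo-first: active dosing from 14 × 7 = day 98 to 26 × 7 = day 182 after the review.

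**Spacing of dosing visits.** Period 1 has weeks 0, 2, 4 and 8, ending at week 12. Period 2 has weeks 14, 16, 18 and 22, ending at week 26. The gaps are 2, 2, 4 and 4 weeks in each period. With a check at every dosing visit, the longest time from check to dose is 4 × 7 = 28 days in both sequences.

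**Does other text close the gap?**

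| Text | What it covers | What it leaves open |
|---|---|---|
| Inclusion (c) | Birth control and an initial negative test | No later check is written |
| Exclusion (t) and the exclusion in Safety/Tolerability | Pregnancy that is confirmed, intended or planned | A lapse in a woman neither pregnant nor planning pregnancy |
| Inclusion (e) | Ability to comply with visits, treatment plans and blood draws | Does not name contraception |
| Assessments repeated at baseline 2 | Possibly a pregnancy test | A negative test does not show current contraception |
| Counselling, REMS training, visits 2-4 weeks apart, discretionary labs | Real safeguards | None is a recorded check or a dosing condition |

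The baseline-2 entry is ambiguous. Screening/Enrollment introduces the baseline assessments as including labs and then says the assessments are repeated, which could include the pregnancy test. The following sentences tie the named labs to baseline and make others discretionary, and Table 2 lists none.

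**Exposure lost if medication is withheld.**

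- Resolved by the next visit: 2/12 = 17% of a period if withheld at week 2, 14 or 16; 4/12 = 33% if withheld at week 4, 8, 18 or 22.
- Never resolved: at most 12 − 2 = 10 weeks in period 1 (from week 2) and 26 − 14 = 12 weeks in period 2 (from week 14).
- Withheld from week 8 to 12 or week 22 to 26: 28 days, the whole EDE window of the primary outcome.
- Restarting under the weekly titration: four doses at one week each put 3 weeks below the top dose, for a participant who needs the top dose.

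**The case against.** The strongest objection is that this is an absence read from a published protocol paper. The trial runs under an approved institutional protocol with a Data Safety Monitoring Board, and the consent pages are not in the text available here. Visit-level contraception duties may sit in those documents. That stands, and it limits how far the point can go.

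Existing text also covers much of the path to harm. Birth control is mandatory at entry, and the sentence encouraging its use can be read as counselling added to that requirement. The exclusion for confirmed or intended pregnancy carries no time limit. The pregnancy test may be repeated at baseline 2. All of this stands, and it leaves a narrow gap.

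The emphasis on week 14 should also be modest. A lapse can occur in either sequence, and a blinded physician must treat every woman as possibly on active drug from week 0. Week 14 matters because the interval is longer.

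Three stronger readings are tempting and are not supported:

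- A reader might infer that the plan allows pregnant women to be dosed, or that no pregnancy test precedes the crossover. The exclusion wording speaks against the first, and the second is unclear rather than established.
- A reader might turn the intervals into a share of drug time that is unchecked. Any such share depends on a threshold the documents do not give. Taking 28 days merely reflects the visit spacing, so it would describe the calendar and not the risk.
- A reader might multiply the 1 in 500 cleft risk into an expected harm. That figure applies to first-trimester exposure, and the documents give no rate of lapse or pregnancy.

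**Conclusion.** The point holds as a minor safety improvement that is cheap to make. The on-treatment wording is weaker than the plan's own entry condition, and nothing visible makes birth control a condition of dosing after week 0. The measurable size is the interval: 0 to 84 days from last written review to active dosing in the active-first sequence, and 98 to 182 days in the placebo-first sequence. The number of lapses or exposed pregnancies cannot be estimated, and none is claimed.

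This rests on three assumptions: the first study visit is at week 0, as Table 2 indicates; the study physician is blinded; and the consent form and institutional file do not already contain an equivalent rule. If they do, the change only brings this text into line with them.

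**What to change.** In Safety/Tolerability, replace the sentence that encourages contraception with:

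> Women of child-bearing potential must use adequate birth control throughout both treatment periods. The study physician asks about and records this before study medication is given at each dosing visit (Medication Visits 1-4 and 6-9), including Medication Visit 6, in both sequences. While it is not met, study medication (active or placebo) is withheld, and the participant stays in follow-up and in the ITT analysis. Dosing then restarts under the weekly titration in Methods Procedure, as tolerated.

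In Screening/Enrollment, state whether the baseline-2 assessments include the pregnancy test.

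The new text restates only the birth-control part of inclusion (c), because an initial pregnancy test cannot be met again later. The rule is the same for both sequences and for active and placebo, so applying it does not reveal treatment.

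**Cost.** A few sentences, and one recorded question at seven visits already scheduled (weeks 2, 4, 8, 14, 16, 18 and 22); week 0 is covered by the first-visit review. The birth-control rule adds no visit or test. The rare participant with a lapse loses exposure as worked out above, plus re-titration time, and the loss can fall across the whole 28-day primary-outcome window. The question relies on self-report and does not detect pregnancy, which is why the baseline-2 test should be clarified as well.

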Measures include demographic data, vital signs (including heart rate, blood pressure, weight), Eating Disorder Examination (EDE),⁴⁵ Eating Disorder Examination Questionnaire (EDE-Q),⁴⁶ Yale-Brown Obsessive Compulsive Scale for Binge Eating (YBOCS-BE),⁴⁷ Three Factor Eating Questionnaire (TFEQ),⁴⁸ Yale Food Addiction Scale (YFAS), ⁴⁹ Binge Eating Scale (BES),⁵⁰ and Patient Health Questionnaire (PHQ-9). ⁵¹ Major assessment points are scheduled prior to randomization (baseline 1), after 12 weeks of treatment (post-treatment 1), prior to the crossover (baseline 2), after the 12 week crossover (post-treatment 2), and after follow-up months 1 (follow-up 1) and 2 (follow-up 2). In addition, vital signs are recorded at each of the 12 medication visits. Weekly online binge trackers are used to record participants' self-reported binge and/or purge episodes.

The primary and secondary study efficacy outcomes are listed in Table 1.

Table 1. Finnary and secondary study enfeacy outcomes
Primary study outcome
Number of binge eating days per week from EDE (average over 28 days)
Secondary study outcomes
Number of binge eating episodes from EDE (average per 28 days)
Abstinence (no binge eating episodes) from EDE over past 28 days
Binge Eating Scale (BES)
Patient Health Questionnaire (PHQ-9)
Eating Disorder Examination Questionnaire (EDE-Q)
Dietary restraint subscale
Eating concern subscale
Weight concern subscale
Shape concern subscale
Global Score for all subscales
Three-Factor Eating Questionnaire (TFEQ)
Cognitive restraint of eating subscale
Disinhibition score subscale
Hunger score subscale
Yale-Brown Obsessive Compulsive Scale modified for binge eating (YBOCS-BE)
Yale Food Addiction Scale (YFAS)

Table 1. Primary and secondary study efficacy outcomes

Data Analysis Plan

The primary outcome measure will be the average number of binge eating days per week, as assessed by the EDE. Secondary outcome measures include the average number of binge eating episodes and percentage abstinence from binge eating. Throughout the study, weekly online binge trackers are used to record participants' binge and/or purge episodes per week per patient report. Vitals (weight, heart rate, blood pressure) and side effects will be assessed at each visit to ensure safety. See Table 2. In addition, any treatment-emergent adverse events will be recorded.

Table 2. Assessment Schedule

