Measures	Baseline1 (Wk0)	Med Visit 1 (Wk0)	Med Visit 2 (Wk2)	Med Visit 3 (Wk4)	Med Visit 4 (Wk8)	Med Visit 5 PT1 (Wk12)	Med Visit 6 BL2 (Wk14)	Med Visit 7 (Wk16)	Med Visit 8 (Wk18)	Med Visit 9 (Wk22)	Med Visit 10 PT2 (Wk26)	Follow Up Med Visit 11 (Wk30)	Follow Up Med Visit 12 (Wk34)
Informed Consent	Х												
Demographics	Х												
Vitals (Weight/HR/BP) & Side Effects	х	Х	Х	Х	Х	Х	Х	X	Х	Х	Х	X	Х
EDE	Х					Х	Х				Х		
BES	Х					Х	Х				Х		
PHQ-9	Х					Х	Х				Х		
EDE-Q	Х					Х	Х				Х		

Study Protocol And Rationale Phentermine-Topiramate ER

TFEQ	Х			Х	Х		Х	
YBOCS-BE	Х			Х	Х		Х	
YFAS	Х			Х	Х		Х	

*Abbreviation Key: Eating Disorder Examination (EDE), Binge Eating Scale (BES), Patient Health Questionnaire (PHQ-9), Eating Disorder Examination Questionnaire (EDE-Q), Three Factor Eating Questionnaire (TFEQ), Yale-Brown Obsessive Compulsive Scale for Binge Eating (YBOCS-BE), and Yale Food Addiction (YFAS), Baseline Assessment (BL1, BL2), Post-Treatment Assessment (PT1, PT2). Crossover occurs at Medication Visit 6 with twoweek washout prior.

Primary and secondary study outcomes will be compared using intention-to-treat (ITT) analysis for all randomized patients. Mixed-effects models with fixed effects for treatment, follow-up period, treatment by period (interaction representing carry-over effect), and eating disorder diagnosis (used to stratify randomization) will be used to estimate the treatment effect. Mixedeffects models include subject-level random effects to account for repeated measurements within subjects. Non-significant treatment by period interaction ($p \ge 0.05$) will be removed from the model before estimating the final treatment effect. In the case of a significant treatment by period interaction (p < 0.05) the analysis will revert to that of a standard parallel arm randomized trial using data from the first period only. A p-value of less than 0.05 is considered statistically significant and the Kenward-Roger degrees of freedom approximation will be used in tests of significance from mixed models.

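### Depression is a disclosed side effect, yet the PHQ-9 is taken on treatment only at the end of each 12-week period; adding it at existing visits is a cheap safety gain

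*Combined protocol and SAP*

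**What the plan says.** - **Known risk.** In Safety/Tolerability, the side effects that participants are told about at the top doses include "dizziness, insomnia, nausea, depression, blurred vision, low potassium, and angle closure glaucoma".
- **Entry limit.** The exclusion criteria bar anyone with "current suicidal ideation or baseline Patient Health Questionnaire (PHQ-9) score of 20 or greater".
- **Timing of the PHQ-9.** Table 2 marks it at Baseline 1 (Wk0), post-treatment 1 (Wk12), baseline 2 (Wk14) and post-treatment 2 (Wk26). Screening/Enrollment gives the same pattern in words: the "assessments are completed again after treatment in the first medication group, at baseline 2 prior to crossing over to the second medication group", and once more after the second treatment.
- **Role of the PHQ-9.** Measures states that "The primary and secondary study efficacy outcomes are listed in Table 1", and the PHQ-9 is in that table as a secondary outcome. No use of it as a safety measure during treatment is described.
- **General safety cover.** Under Data Analysis Plan, "side effects will be assessed at each visit to ensure safety" and "any treatment-emergent adverse events will be recorded". The Table 2 row "Vitals (Weight/HR/BP) & Side Effects" is marked at every visit. Dose steps depend on tolerability (Methods, Procedure), the dose is lowered for intolerable side effects (Discussion), and a data safety monitoring board oversees the study (Methods, Procedure).
- **Symptom-specific rule.** Blurred vision or eye pain has one: "In such cases Qsymia is discontinued and patients are referred for intra-ocular pressure measurement within one day of symptom onset". No corresponding rule for mood or suicidal ideation is described, and neither is any assessment at early termination.

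**The concern.** The investigators treat mood as relevant to safety: they warn of depression and set a numeric PHQ-9 limit at entry. The Discussion presents the protocol as built to keep participant risk as low as possible. Once dosing starts, however, the scale that guarded entry is not used again until the period ends. Low mood or suicidal ideation that does not surface in the general side-effect assessment could go unscored for most of a treatment period. A participant who stops early may leave with no PHQ-9 after baseline for that period. The introduction notes that mood disorders often accompany these diagnoses, and the entry rule admits scores up to 19, so some participants may start close to the limit.

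What is at stake is participant safety and the quality of the safety data on mood. The primary efficacy comparison is not affected.

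**Working it through.** **Inputs**
- Treatment-period visits (Table 2): Wk0, 2, 4, 8, 12 in period 1; Wk14, 16, 18, 22, 26 in period 2.
- PHQ-9 (Table 2): Wk0, 12, 14, 26.
- Titration (Methods, Procedure): four doses, one step per week over a 4-week ramp.
- Enrolment and dropout (Sample Size and Statistical Power): 24 evaluable, 20% dropout, 30 enrolled. This reproduces: 24 / (1 − 0.20) = 30.

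**1. On-treatment PHQ-9 readings now.** Wk0 and Wk14 come before dosing and serve as each period's baseline. That leaves Wk12 in period 1 and Wk26 in period 2: 1 reading per period, or 2 of the 8 visits after dosing starts.

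**2. Longest interval between PHQ-9 forms within a period now.** 12 − 0 = 12 weeks; 26 − 14 = 12 weeks.

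**3. Interval between side-effect assessments now.** The gaps are 2, 2, 4 and 4 weeks in each period, so the maximum is 4 weeks. The 12 weeks in step 2 is therefore a gap between forms; it is not a gap in safety review.

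**4. Time from top dose to next PHQ-9 for a fully titrated participant.** The top dose is reached after three weekly steps (Wk3, Wk17) or at the latest by the end of the ramp (Wk4, Wk18).
- Now: 12 − 3 = 9 or 12 − 4 = 8 weeks (26 − 17 = 9 or 26 − 18 = 8).
- With the PHQ-9 at Wk4 and Wk18: 4 − 3 = 1 or 4 − 4 = 0 weeks (18 − 17 = 1 or 18 − 18 = 0).

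Again, these are intervals to the next form.

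**5. With the PHQ-9 added at Wk2, 4, 8, 16, 18 and 22.** Readings fall at Wk2, 4, 8, 12 and Wk16, 18, 22, 26: 4 per period, at 8 of 8 visits. The gaps become 2, 2, 4 and 4 weeks, maximum 4.

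**6. Forms added.** Six per participant if Wk2 is still ahead, 3 for someone at the crossover (Wk14), 0 for someone past Wk22. The most possible is 6 × 30 = 180. Trial Status says recruitment began in 2015, so the real total is lower to the extent that participants have already passed these visits.

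**7. Early-termination forms.** At the planned dropout, 0.20 × 30 = 6. This is an expectation and could be exceeded. The introduction cites side-effect dropout of up to 50% in topiramate studies; at that rate the count would be 0.50 × 30 = 15.

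**8. Lighter option.** Adding only Wk4, 8, 18 and 22 gives 3 readings per period, gaps of 4, 4 and 4 weeks, and at most 4 × 30 = 120 forms. The longest gap is the same; what is lost is the reading during early titration.

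**The case against.** The strongest reply is that mood is already covered. Side effects are assessed at four on-treatment visits per period, dose increases depend on tolerability, adverse events are recorded, a board monitors the trial, and the study is run in a psychiatry department. Entry excludes bipolar disorder, schizophrenia, suicidal ideation and high PHQ-9 scores. The PHQ-9 is itself self-report, so a patient who hides ideation from the physician may hide it on the form too. All of this stands. It limits the size of the point but does not supply a scored mood check during treatment.

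Three stronger readings are tempting, and the documents do not support them.
- **That the every-visit review is unstructured.** Its format is not given. A checklist that names depression fits the text as well as open questioning does.
- **That the trial has no suicidality procedure.** This is a published protocol article about a study with an approved protocol on file, and a procedure may be stated there. Only its absence from this document can be claimed.
- **That the eye-symptom rule shows mood was overlooked.** Insomnia, nausea and dizziness have no stop-and-refer rule either. The eye rule shows the form such a rule can take and nothing more.

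It is also fair to say that no harm has been demonstrated. The documents give no depression rate. Appearing in the side-effect list does not imply one, since the same list includes an event put at less than 1 in 1000.

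**Conclusion.** The point holds as a low-cost safety improvement. The only mood instrument the plan names is used on treatment once per 12-week period, at its end, although depression is a disclosed side effect and the same scale guards entry. Using it at visits that already exist would give 4 readings per period in place of 1, with a longest gap of 4 weeks in place of 12.

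This rests on Table 2, whose PHQ-9 row agrees with the text in Screening/Enrollment. It does not depend on whether a suicidality procedure exists elsewhere; only the action-rule part of the remedy does. A reader might infer that mood goes unwatched for 12 weeks, or that a given number of events would be caught earlier. The every-visit assessments contradict the first, and the documents give no basis for the second. Sample size, power and the primary analysis are unaffected.

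**What to change.** Amend Table 2 as follows.
- Mark the PHQ-9 at the Wk2, 4, 8, 16, 18 and 22 visits, for participants who have not yet passed them.
- Add a PHQ-9 at early termination where the patient attends.
- Have the study physician review the form at the visit.
- Use the entry criterion (suicidal ideation, or PHQ-9 of 20 or more) as the trigger for clinical assessment and a decision on reducing or stopping study drug. If the approved protocol file already has a suicidality procedure, state that one here instead.
- Keep Wk12 and Wk26 as the efficacy time points for the PHQ-9.

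The cost is one amendment and no extra scheduled visits. It adds up to 6 short forms per participant (at most 180 for 30), about 6 early-termination forms if dropout is 20% and more if it is higher, and physician time to review and respond. Participants seen before the amendment will have fewer PHQ-9 readings than those seen after it, and the report should say so.

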The study was reviewed and approved by the Institutional Review Board of Stanford University Medical Center. The research is being conducted in the Department of Psychiatry and Behavioral Sciences and is carefully monitored (protocol # 31390) by a Data Safety Monitoring Board at Stanford University. This is a randomized double-blinded placebo-controlled crossover trial totaling 34 weeks in length with ongoing enrollment of adults with BED (up to n = 15) and BN (up to n= 15). Patients are randomized to identical appearing placebo or Qsymia with 4 standard FDA-approved doses of phentermine/topiramate ER: 3.75mg/23mg; 7.5mg/46mg; 11.25mg/69 mg; and 15mg/92mg. The oral administration follows a weekly titration increase as follows: The four doses of Qsymia are titrated in a gradual fashion weekly over the course of four weeks, beginning with the lowest standard dose of phentermine/topiramate (3.75 mg/23 mg) up to the highest standard dose (15mg/92 mg) as tolerated. Each week of the 4-week ramp up period, the dose is increased to the next standard dose, provided no major side effects are reported. The final dose prescribed will be the minimum dose at which effects are seen and side effects are tolerable. Patients are randomized to 12 weeks of treatment with Qsymia or placebo, then a 2-week washout followed by a crossover of 12 weeks (total 26 weeks) and a final 8 weeks of follow-up while off medications, totaling 34 weeks (Figure 1). The washout period of two weeks was chosen to account for sufficient time to allow completion of at least five half lives, given a halflife in plasma of twenty hours for phentermine and sixty-five hours for topiramate. Per the protocol, subjects will be expected to attend 12 study visits spaced 2-4 weeks apart. Compensation in the form of giftcards of twenty US dollars will be given for completion of each assessment: post-treatment 1, post-treatment 2, follow-up 1 and 2 assessments. For participants who complete all four assessments, an additional twenty US dollars will be given.

Sample Size and Statistical Power

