This RCT crossover study is designed to test for a clinically meaningful difference in number of binge days (primary study outcome) when comparing drug to placebo. Assuming a standard paired t-test we estimated that for 80% power, a significance level of 0.05, and a standardized treatment effect size of 0.6 a total of 24 subjects are required. The standardized treatment effect of 0.6 was estimated based on previous studies of topiramate. ^{43, 27} To account for an estimated drop out rate of 20%, the minimum sample size requirement was inflated accordingly to 30 subjects. The paired t-test requires differences to be normally distributed. Should the differences be substantially non-normal, the t-test would no longer be the optimal test with respect to power and the estimated sample size would be slightly conservative."

Randomization Procedure

Eligible participants are randomly assigned to medication group 1 or 2; a cross-over protocol follows the first phase of the trial. This is to be done by randomization as they are sequentially

determined to be eligible for the study. Eating disorder diagnoses (BN and BED) are being recruited and randomized separately to ensure even distribution of diagnoses in each medication group. Five blocks of six permutation identifications were created and a treatment group assigned to each ID. Each treatment group will be shuffled within each block using the RAND function in Excel (Microsoft). This schedule and randomization was determined by the study research coordinator and reviewed by a statistician prior to study initiation.

Participants: Inclusion/Exclusion Criteria

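### Is the Baseline 2 EDE spoiled because its 28-day look-back reaches past the two-week washout into period-1 dosing?

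*Combined protocol and SAP*

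**What the plan says.** All places are in the combined protocol and SAP.

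- **Outcome window.** Measures, Table 1 defines the primary outcome as "Number of binge eating days per week from EDE (average over 28 days"). Abstinence also uses a 28-day look-back. No different window is given for Baseline 2.
- **Timing.** Table 2 marks the EDE at Baseline 1 (Wk0), PT1 (Wk12), "Med Visit 6 BL2 (Wk14") and PT2 (Wk26). Its footnote reads "Crossover occurs at Medication Visit 6 with twoweek washout prior". Screening/Enrollment likewise repeats the assessments "at baseline 2 prior to crossing over to the second medication group".
- **Washout.** Methods, Procedure justifies two weeks as at least five half-lives, "given a halflife in plasma of twenty hours for phentermine and sixty-five hours for topiramate".
- **Analysis.** The Data Analysis Plan fits a mixed model with treatment, period, "treatment by period (interaction representing carry-over effect") and diagnosis. Subject random effects are included to "account for repeated measurements within subjects". The visits that enter are not listed, and no Baseline 2 term is named.
- **Other washout data.** Weekly online trackers record self-reported episodes throughout the study.

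**The concern.** A visit named Baseline 2, placed after a washout, suggests an off-treatment score. With a 28-day look-back and a 14-day washout it cannot be one for participants who took drug first. Even if the drug effect ended with the last dose, the two sequences would differ at Baseline 2, and a reader could mistake that difference for carry-over. If someone used the score as the starting point for period-2 change, the treatment contrast would be distorted.

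The point looks sharper because the Discussion names carry-over as a limitation and says the analysis will assess it. As Table 2 reads, this is also the only EDE in either sequence covering any of the first ten weeks after drug is stopped. A count restricted to the washout days, taken at the same interview, appears to be a cheap improvement.

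**Working it through.** **The plan's own figures.** Five half-lives are 5 × 65 h = 325 h = 13.5 days for topiramate and 5 × 20 h = 100 h = 4.2 days for phentermine. Both fit in 14 days. For the sample size ("a total of 24 subjects are required"), an exact two-sided paired t-test at effect size 0.6 and level 0.05 gives power 0.804 with n = 24 and 0.785 with n = 23. Then 24/0.80 = 30. Both statements reproduce, and 24 completers give 12 per sequence.

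**Windows (days counted from the start of period 1, visits on time).**

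| EDE | Look-back | Days on period treatment | Washout days |
|---|---|---|---|
| PT1, Wk12 | days 57-84 | 28 | 0 |
| Baseline 2, Wk14 | days 71-98 | 14 | 14 |
| PT2, Wk26 | days 155-182 | 28 | 0 |

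Baseline 2 shares days 71-84 with PT1.

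**What the mixture does.** Let D be the drug effect in binge days per week and f the fraction that persists through washout. The sequence difference at Baseline 2 is 0.5D + 0.5fD, which runs from 0.5D (f = 0) to 1.0D (f = 1). A washout-only count would give fD, from 0 to 1.0D.

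**What it could do to the treatment estimate.** If Baseline 2 served as the period-2 change baseline with f = 0, the period-2 contrast would be D + 0.5D = 1.5D, and the two-period average (1.0D + 1.5D)/2 = 1.25D. No section proposes that analysis. Comparing PT1 with PT2 leaves the estimate free of this mixture, at 1.00D.

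**What the scheduled data already give.** Write a, b and c for the rates in Wk8-10, Wk10-12 and Wk12-14. Then PT1 = (a + b)/2 and Baseline 2 = (b + c)/2, so

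2 × (Baseline 2 − PT1) = c − a.

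This is washout minus on-treatment, with the shared fortnight cancelled if both interviews score it alike.

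**Gain from a separate 14-day count.** Assumptions not in the documents: 3.5 binge days per week (daily probability 0.5) and independent days. The variance of a weekly rate over n days is then 49 × 0.25/n, which is 0.4375 for 28 days and 0.875 for 14 days. The 95% half-width for a sequence difference is 2.074 × SD × √(2/12).

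| Change score | SD, stable individual rates | Half-width | SD, true rates shift with SD 1 | Half-width |
|---|---|---|---|---|
| 14-day count − PT1 | √(0.875 + 0.4375) = 1.146 | 0.97 | √(1.3125 + 1) = 1.521 | 1.29 |
| 2 × (Baseline 2 − PT1) | √(2 × 0.875) = 1.323 | 1.12 | √(1.75 + 1) = 1.658 | 1.40 |

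The SD ratios are 1.323/1.146 = 1.15 and 1.658/1.521 = 1.09, so the standard error falls by about 13% or 8%.

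Comparing raw levels between sequences makes the gain look far larger. With between-subject SD 1.0 to 2.0, the separation 2 × SD28/SD14 is 2 × 1.20/1.37 = 1.75 up to 2 × 2.11/2.21 = 1.91. That comparison ignores each participant's own PT1 score, so it is the wrong benchmark.

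**Is the washout fortnight drug-free?** By first-order decay at 65 h, mean topiramate over the 14 days is (1 − e^(−336k))/(336k) = 0.27 of its starting level, with k = ln 2/65. The mean is 0.47 in the first week and 0.08 in the second. A washout-only count is cleaner, but not clean.

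**The case for a change.** The best case for acting is that the calendar fact is certain and the remedy is small: one more count at an interview already scheduled, and one descriptive table. Carry-over decides whether period 2 is kept, so direct evidence on offset would help readers interpret the interaction test. The plan also leaves the modelled visits unlisted, and one sentence excluding Baseline 2 would rule out the 1.5D misuse.

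Part of this stands. Baseline 2 is not an off-drug score in the drug-first sequence, and the list of visits is missing. The rest is weaker:

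- A washout visit belongs to neither level of the treatment factor, so taking PT1 and PT2 as the outcomes is the natural reading of the model.
- The extra count would decide little. With D near 1 day per week, no carry-over and full carry-over differ by about 1.0, against half-widths of 0.97 to 1.29. It also cannot speak to the PT2 window, which opens 22 − 12 = 10 weeks after the last period-1 dose.
- The documents do not show whether EDE records allow a 14-day count, and recruitment has run since 2015, so sources could end up mixed across participants.
- The Discussion assigns symptoms after stopping medication to the 8-week follow-up. Measures lists both follow-ups as major assessment points, but Table 2 marks no EDE there. That mismatch is a separate matter.

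One limit remains: doubling the change does not work for abstinence, which is not an average over days.

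**Conclusion.** No change to the plan is needed. Half of the Baseline 2 window (14 of 28 days) is period-1 treatment, but no stated analysis relies on that score and the PT1-versus-PT2 estimate is unaffected. Leaving Baseline 2 out of the model as a baseline, covariate or repeated outcome is what a competent analyst would do unprompted.

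Early offset in binge days can be described by twice the Baseline 2 minus PT1 change, with the Wk12-14 trackers as self-reported support. A dedicated washout count would trim the standard error by roughly 8-13% and change no decision.

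The conclusion rests on visits at their nominal weeks, dosing to Wk12, and PT1 and PT2 as the modelled outcomes. The precision figures rest on the assumed binge rate, independent days, the assumed shift in true rates and 12 participants per sequence.
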